1.0 GOALS AND OBJECTIVES (SCIENTIFIC AIMS)

In patients with relapsed or relapsed/refractory multiple myeloma (MM):

Phase I

Primary Objectives:

- To determine the maximum tolerated dose (MTD) and recommended phase II dose (RP2D) of leflunomide, when given as a single agent.
- To assess the safety and tolerability of leflunomide at each dose level by evaluation of toxicities including: type, frequency, severity, attribution, time course and duration.

Phase II

Primary Objective:

- To evaluate the anti-myeloma activity of leflunomide, when given as a single agent, as assessed by overall response rate (ORR).

Secondary Objectives:

- To obtain estimates of:
 - Response duration
 - Clinical benefit response
 - Overall survival and
 - Progression-free survival.

Clinical Pharmacology Objectives (Phase I and II)

- To characterize the relationship between serum concentration of the active leflunomide metabolite, teriflunomide (A77 1726), and toxicity.
- To assess the relationship between serum concentration of the active leflunomide metabolite, teriflunomide A77 1726), and disease response.

Exploratory Ex-Vivo and Molecular Objectives (Phase I and II)

- To explore the relationship between polymorphisms in the *CYP1A2*, *CYP2C19*, or *DHODH* genes and toxicity/response. *CYP1A2*, *CYP2C19* are the hepatic enzymes responsible for leflunomide metabolism.
- To explore the *ex vivo* cytotoxicity of leflunomide toward primary MM cells, in order to evaluate whether individual *ex vivo* leflunomide response might be a useful predictor of therapeutic response.
- To explore the potential additive or synergistic effects of combining leflunomide with other classes of FDA-approved drugs. The classes include HDAC inhibitors, immunomodulatory drugs [IMiDs], proteasome inhibitors, steroid hormones, and antibody therapeutics such as the CD38 antibody daratumumab.
- To generate a preliminary RNA/miRNA and DNA methylation signature associated with response of MM cells to leflunomide *in vivo* (mRNA/miRNA and DNA methylation, phase II only) and teriflunomide *ex vivo* (mRNA/miRNA).

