⁺: Although under this scenario escalating to the next higher dose level is suggested, additional patients can be accrued to the current level -up to n=6 patients.
^{**}: Patients treated on a higher dose will have their treatment modified to the dose below the dose level with 2 DLTs, if pending patients have DLT.

Phase II Design

Following completion of the phase I portion of the study and identification of the RP2D, the phase II portion of the study will be initiated. Recent studies evaluating daratumumab, a CD38 monoclonal antibody, as monotherapy for relapsed/refractory multiple myeloma were recently published [39, 40] and have led to FDA approval of this agent. One study included patients with relapsed multiple myeloma treated with at least three lines of therapy while the other included patients treated with at least two prior lines of treatment. Treatment with daratumumab as a single agent lead to an overall response rate of 29.2% and 36% respectively in each of these studies. In both studies, the agent investigated was well tolerated but required IV dosing once weekly for 8 doses, followed by twice-monthly doses for 8 doses and then monthly thereafter. We suspect leflunomide to be similarly well tolerated but with a more convenient dosing schedule. Because we are including patients who have received at least three prior lines of treatment, we will target an overall response rate of 30% for the phase II portion of the study.

This single-center, single arm phase II trial will implement a Simon Two-Stage Optimal Design [2, 3]. to evaluate the anti-myeloma activity of leflunomide, when given as a single agent, as assessed by overall response rate (ORR), in patients with relapsed or relapsed/refractory MM. The phase II portion of the study is expected to enroll a minimum of 19 and a maximum of 39 patients. The sample size is based on the desire to discriminate a promising ORR of 30% from a disappointing response rate of 15% using a type I error rate of 0.10 and power of 80%.

At stage 1, 19 patients will be entered on the study. If ≤ 3 responses are seen, the study will be terminated. If at least 4 patients achieve response, the trial will continue to the second stage. The 6 patients treated at the RP2D in the phase I portion will be evaluated as part of this phase II group. The probability of early stopping after the first stage is 0.68.

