For the studies combining teriflunomide with other agents *ex vivo*, combination Index (CI) values will be calculated using the CalcuSyn software program (Biosoft, Ferguson) to determine which of the compounds work synergistically, if any. A combination index of < 0.9 indicates synergism, whereas $CI = 0.9$ to 1.1 indicates additive effects. $CI > 1.1$ indicates antagonism. Isobogram diagrams will be generated that show the varying combination treatments and the ratio where maximal synergy is obtained.

The miRNA/mRNA expression profile and DNA methylation data will be used to identify the miRNA/mRNA and differential methylated regions (DMRs) that show significant differences between responders and non-responders after leflunomide treatment. For miRNA/RNA profiling, fold changes >3 with an FDR <0.05 will be considered significant. Assuming the dispersion of genes across replicates is 0.2 and minimum average expression is 10 reads per gene, 10 samples in each group (responder vs. non-responder) should have 89% power to detect a 3-fold difference between groups at an FDR level of 0.05.

The major goal of RNA-seq/miRNA-seq/RRBS-seq is to predict potential responders based on pre-treatment genomic profiling. A logistic regression-based algorithm with risk score formula described previously [46] will be used to build a classifier for response prediction. Differentially expressed miRNA/mRNA and DMRs together with other known clinical risk factors will be included in the

multivariable logistic regression model. The performance of the identified classifier will be evaluated with leave one out cross validation (LOOCV). Specifically, for each iteration -as part of a random selection process, one sample will be left out as the test sample; the remaining samples will be used to build a classifier, and the classifier will be used to predict the response status of the test sample. The sensitivity and specificity of the classifier will be calculated, as well as receiver operating characteristic (ROC) curve and area under the curve (AUC) to evaluate its accuracy.

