Another goal of the genomic profiling is to identify potential new pathways to complement leflunomide treatment. We will compare the miRNA/mRNA/methylation profiles between responders and non-responders. Differentially expressed genes will be used to identify pathways that are activated in non-responders, which will provide insights into possible complementary therapy. Gene ontology (GO) and KEGG pathways will be analyzed using DAVID and GSEA. Pathways and GO that are activated in non-responders will be sorted by their multiple comparison adjusted p-value. Potential miRNA targets will be identified using TargetScan and the enrichment of GO and pathways will be identified as well. The NCI connectivity map, an online resource to predict therapeutic efficacy based on pathway based gene expression profiles, will also be explored to determine the complimentary therapeutic agents for leflunomide.

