Illumina adapters. The cDNA fragments of 130-280 bp will be isolated from polyacrylamide-urea gels. In addition, all small RNAs of 15-52 nucleotides will be selected separately and used to make small RNA libraries following the Illumina's protocol. The libraries will be quantified using qPCR and loaded to cBot for clustering generation. Sequencing will be performed on a Hiseq 2500, and image processing and base calling conducted using Illumina's pipeline. For mRNA-seq, sequence reads will be mapped to the human genome (hg19) using TopHat and the frequency of Refseq genes will be counted with customized R scripts. For miRNA-seq, sequences will be adapter-trimmed and aligned to hg19 genome using Novoalign, and miRNA expression level will be counted as previously described. The raw counts will then be normalized and compared using the Bioconductor package "edgeR". Gene ontology (GO) and pathways will be analyzed using DAVID (Database for Annotation, Visualization, and Integrated Discovery), an online bioinformatic resource for functional interpretation of large lists of genes. Pathways and GO that correlate with response will be sorted by their multiple comparison adjusted p value. Potential miRNA targets will be identified using TargetScan and their functional annotation will be done using DAVID.

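### The 89% power quoted for the expression analysis is for the FDR test alone; under the plan's two-part rule, power at a true 3-fold difference is about 50%

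*Combined protocol and SAP*

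**What the plan says.** Section 13.5, under ex vivo and molecular studies, compares responders with non-responders after leflunomide. The calling rule for miRNA and RNA is "fold changes >3 with an FDR <0.05 will be considered significant".

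The next sentence gives the power. Its inputs are "Assuming the dispersion of genes across replicates is 0.2" and "minimum average expression is 10 reads per gene", and its result is that "10 samples in each group (responder vs. non-responder) should have 89% power to detect a 3-fold difference", at an FDR of 0.05. It does not mention the fold-change cut-off, and neither document section nor appendix gives power for the two criteria together.

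Appendix B names the method: "The raw counts will then be normalized and compared using the Bioconductor package" edgeR, which models counts as negative binomial. The called genes are used later in section 13.5: "Differentially expressed genes will be used to identify pathways that are activated in non-responders". Section 1.0 lists the work among the exploratory objectives: "To generate a preliminary RNA/miRNA and DNA methylation signature associated with response of MM cells to leflunomide".

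**The concern.** The decision rule has two conditions and the power figure covers one. The true effect assumed for power (3-fold) equals the cut-off that the estimate must exceed. An estimate centred on a threshold lands above it about half the time, so no sample size gives high power at that effect.

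A reader will take 89% as the chance that a gene with a true 3-fold difference is called. Under the plan's rule that chance is about 50%. The called genes feed the pathway analysis. Section 13.5 also puts differential transcripts into the response classifier, but it does not say that the pre-treatment classifier draws on this list, so that link is only plausible. The stakes are limited, because the signature is preliminary and no trial decision depends on it.

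**Working it through.** **Inputs from section 13.5.** n = 10 per group, dispersion φ = 0.2, true ratio 3, FDR 0.05, 10 reads. Because 10 reads can be read in two ways, both were run: as the lower group's mean (10 vs 30) and as the average of both groups (5 vs 15). **Assumption, not in the plan:** the share π of genes that truly change, varied from 0.5% to 5%. The fold-change part is read as a filter on the observed ratio.

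**Step 1: precision of the log ratio.** SE² = [(1/μ₁ + φ) + (1/μ₂ + φ)]/n.
- 10 vs 30: (0.1 + 0.2 + 0.0333 + 0.2)/10 = 0.0533, so SE = 0.231 and ln 3/SE = 1.0986/0.231 = 4.76.
- 5 vs 15: (0.2 + 0.2 + 0.0667 + 0.2)/10 = 0.0667, so SE = 0.258 and ln 3/SE = 4.26.

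**Step 2: the plan's 89%, FDR test alone.** The per-gene two-sided level is α = (0.05/0.95) × π × power/(1 − π), solved together with power = Φ(ln 3/SE − z at 1 − α/2).

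| π | 10 vs 30 | 5 vs 15 |
|---|---|---|
| 0.5% | 0.858 | 0.697 |
| 1% | 0.897 | 0.764 |
| 2% | 0.929 | 0.824 |
| 5% | 0.960 | 0.890 |

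So 0.89 is obtained at π of about 0.9% (10 vs 30) or 5% (5 vs 15). An exact conditional negative binomial test agrees: 0.894 at π = 1% (10 vs 30) and 0.893 at π = 5% (5 vs 15). The figure is attainable for the FDR test, but the printed inputs do not fix it.

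**Step 3: the two-part rule.** The probability of passing the filter is Φ(ln(true ratio/3)/SE), with the SE recomputed at each true ratio. For example, at 4-fold with a lower mean of 10, SE² = (0.1 + 0.2 + 0.025 + 0.2)/10 = 0.0525, SE = 0.229, ln(4/3) = 0.288, and Φ(1.26) = 0.895. At exactly 3-fold the argument is 0, which gives 0.50 whatever the SE.

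An observed ratio of 3 corresponds to z of about 4.8 or 4.3. The strictest level simulated, α = 2.3e-4, needs only about 3.7. With 10 per group, any gene that passes the filter has therefore already passed the FDR test, and the filter probability is the joint power. Simulation (200,000 negative binomial replicates, dispersion taken as known) confirmed this for Wald and likelihood-ratio tests:

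| True ratio | Lower mean 10 (Wald / LRT) | Average 10 (Wald / LRT) |
|---|---|---|
| 3 | 0.500 / 0.498 | 0.502 / 0.503 |
| 3.5 | 0.751 / 0.750 | 0.723 / 0.726 |
| 4 | 0.897 / 0.898 | 0.863 / 0.864 |

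Exact negative binomial totals give 0.4998 and 0.4993 at 3-fold for the two readings. By the formula, 0.89 is reached at 3.97-fold and 4.17-fold.

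**Step 4: can design changes raise the 3-fold value?** No. With 100 per group (20,000 replicates) the test alone has power 1.000, while the joint power is 0.503 (10 vs 30) and 0.498 (5 vs 15). It also stays at 0.50 with lower-group means of 50 or 500.

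**Step 5: unequal groups.** At a 15% response rate, 39 patients give 0.15 × 39 = 5.85, or about 6 vs 33. Joint power is then 0.48 to 0.52 at 3-fold and 0.87 to 0.91 at 4-fold. The phase II design says "If at least 4 patients achieve response, the trial will continue to the second stage", so stopping at stage 1 leaves at most 3 responders among 19. For 3 vs 16 at α = 5e-4 (about 1% of genes changed), joint power is 0.21 to 0.48 at 3-fold and 0.47 to 0.80 at 4-fold. The range depends on the test, on the reading of 10 reads and on which group has the lower mean. Here the FDR test is often what binds. These figures take the average as the simple mean of the two group means.

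**The case against.** **The sentence names its own criterion.** It says the power is at an FDR level, and 89% can be reproduced on that basis, so nothing is miscalculated. That is true. But the sentence directly follows the two-part rule and is the only power figure for this analysis, so it will be read as the power of that rule, which it is not.

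**The 50% holds only at the boundary.** Any cut on an estimate passes about half the genes lying on it, and above 3-fold more patients or reads do help. This stands, and it is why the 3.5- and 4-fold values belong beside the 50%. The boundary is nevertheless the point at which the plan chose to state its power.

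**Fold change above 3 could mean something else.** The plan does not say observed, and Appendix B describes the edgeR comparison without a cut. Other readings would change the 50% but do not restore the 89%. A formal test against a 3-fold null has power equal to its α at exactly 3-fold. Shrinking the estimates lowers the pass rate: adding 0.125 or 2 counts to each group mean (10 vs 30) gives 0.488 or 0.280.

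**The unequal-split figures are less firm.** This stands in part. If 10 reads is averaged over all samples, 3 vs 16 with the smaller group lower falls to 0.11 (Wald) or 0.17 (LRT) at 3-fold, and 6 vs 33 at 4-fold is about 0.85. Dispersion was also treated as known throughout. The conclusion for 10 vs 10 does not rest on these splits.

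**It is exploratory.** Agreed. That limits the weight of the point but does not make the printed figure correct for the rule.

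**Conclusion.** The concern holds. With 10 per group and dispersion 0.2, the plan's rule has power of about 50% at a true 3-fold difference, against the 89% a reader would infer. Power is 72% to 75% at 3.5-fold and 86% to 90% at 4-fold; the lower ends take 10 reads as the average of both groups, the upper ends as the lower group's mean.

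The 50% rests on reading the cut as a filter on an unshrunken observed ratio. It does not depend on the share of changed genes over the range tried, on the reading of 10 reads, or on sample size once the FDR test is no longer limiting. Whether 89% is right for the FDR test alone cannot be settled from the documents, since it needs an assumed share of roughly 1% to 5%. This is a minor correction to a stated figure in an exploratory analysis.

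**What to change.** Amend the power sentence in section 13.5 to:
- describe 89% as the power of the FDR test alone, and give the assumed share of changed genes;
- say whether 10 reads is the lower group's mean or the average of both groups;
- add the power of the two-part rule with 10 per group: about 50% at 3-fold, 72% to 75% at 3.5-fold and 86% to 90% at 4-fold, or the single values for the reading chosen;
- note that a small responder group, such as 3 vs 16, gives lower power.

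The cost is one or two sentences in the SAP. The fold-change filter, the analysis, the samples collected and the sample size need not change.

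### Section 13.5 does not require response-based feature selection to be repeated inside each cross-validation fold, so the classifier's sensitivity, specificity and AUC may be overstated

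*Combined protocol and SAP*

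**What the plan says.** Section 13.5 (Ex vivo and molecular studies) sets out the classifier in this order.

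1. Find the miRNA/mRNA and differentially methylated regions (DMRs) "that show significant differences between responders and non-responders after leflunomide treatment". No training set or fold is mentioned.
2. Apply a threshold, for RNA only: "For miRNA/RNA profiling, fold changes >3 with an FDR <0.05 will be considered significant". No threshold is given for DMRs.
3. Build a logistic risk-score model: "Differentially expressed miRNA/mRNA and DMRs together with other known clinical risk factors will be included in the" multivariable model.
4. Validate: "The performance of the identified classifier will be evaluated with leave one out cross validation (LOOCV".
5. In each iteration one sample is set aside and "the remaining samples will be used to build a classifier", which then predicts the sample set aside.
6. Report: "The sensitivity and specificity of the classifier will be calculated, as well as receiver operating characteristic (ROC) curve" and AUC.

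Section 13.5 calls prediction of responders from baseline profiles the main aim of the sequencing work. Section 1.0 lists the signature as preliminary, under the exploratory objectives. Appendix B (item 3) describes DMRs differently: methylation is compared between treated and untreated samples, and regions common across the cell lines become candidates. No independent set of patients for validation is described.

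**The concern.** Cross-validation gives an honest estimate only if the held-out patient plays no part in building the model. Here the feature list appears before cross-validation is mentioned, and what is validated is a classifier already identified. If the list was made with every patient's response status, each held-out patient has already helped to choose the features that will predict that patient. Refitting the coefficients on the other patients does not undo this.

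The problem is worst with many candidate features and few patients, which is the situation here. Section 9.4.2 limits the in vivo profiling to participants treated at the RP2D, and the Phase II Design text plans 19 to 39 patients. Sensitivity, specificity and AUC are the only performance figures planned for the signature, and there is no independent set to correct them.

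The specimen time point is also unclear. Features are said to differ between "responders and non-responders after leflunomide treatment", while the aim is prediction before treatment. Specimens are collected both at baseline and after one month of drug.

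**Working it through.** **Inputs from the documents.** Dispersion 0.2, mean 10 reads, 10 per group, 3-fold difference, FDR 0.05, stated power 89% (Section 13.5). Maximum phase II size 39 and response rates of 30% and 15% (Phase II Design): 39 × 0.30 = 11.7, about 12 responders; 39 × 0.15 = 5.85, about 6. Stage 1 has 19 patients, and 4 responders are the fewest that allow continuation.

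**Assumptions, not in the documents.** Number of candidate features (20,000 unless stated), independent features, share of genes truly changed, ridge penalty 1 in the logistic model.

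**1. The plan's own figure.** Power ≈ Φ(log 3 / SE − z), with SE² = (1/10)(1/10 + 0.2) + (1/10)(1/30 + 0.2) = 0.0533, so SE = 0.231 and log 3 / SE = 4.76. With 20,000 genes, 200 of them changed, the per-gene level matching FDR 0.05 is 0.89 × 200 × 0.05 / (0.95 × 19,800) = 0.00047, so z = 3.50 and power ≈ Φ(1.26) = 0.896. Simulation with an exact negative-binomial test gives 88.8% (10,000 genes, 1% changed), 89.1% (20,000, 1%) and 92.2% (10,000, 2%). The stated 89% reproduces if about 1% of genes change. The documents give no figure for classifier performance.

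**2. Pure noise, unfiltered top-k screen (illustration only).** Mean LOOCV AUC for the top 5 / 10 / 20 features:

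| Responders of n | Selected on all samples | Selected in each fold (15 runs each) |
|---|---|---|
| 12 of 39 | 0.985 / 0.997 / 1.000 | 0.46 / 0.53 / 0.35 |
| 6 of 39 | 0.996 / 0.999 / 1.000 | 0.51 / 0.36 / 0.48 |
| 10 of 20 | 0.999 / 1.000 / 1.000 | 0.43 / 0.48 / 0.33 |

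A 60-run nested check (12 of 39, top 10, 5,000 features) gave mean AUC 0.43. Nested LOOCV on noise tends to fall a little below 0.5; it shows no discrimination. A nominal p < 0.001 screen on all samples (about 20,000 × 0.001 = 20 features) gave AUC 1.00.

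**3. Pure noise, the plan's RNA filter.** If no feature is real, FDR control at 0.05 with a valid test also limits the chance of selecting anything to about 5%. Share of runs in which at least one noise feature passed both parts of the filter:

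| Responders of n | Exact test (150 runs) | t-test on log counts | Wald test | Un-nested AUC when a feature passed the exact test |
|---|---|---|---|---|
| 12 of 39 | 0% | 0.5% | 0.5% | none passed |
| 6 of 39 | 1.3% (2 runs) | 19.5% | 77% | 0.93 |
| 10 of 20 | 3.3% (5 runs) | 0.5% | 16.5% | 0.94 |
| 4 of 19 | 3.3% (5 runs) | 16% | 98% | 0.97 |

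The last column rests on very few runs; mean sensitivity there was 0.58 to 0.82. Appendix B names edgeR, which was not simulated, so its pass rate is not known.

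**4. Modest real signals, the plan's RNA filter.** With 5,000 genes, 100 of them truly 2-fold changed (both assumed), a t-test on log counts and 15 runs, un-nested against nested AUC was 0.95 against 0.88 (12 of 39) and 0.99 against 0.85 (6 of 39; the gap is about 0.13 before rounding). A separate set of runs, also with assumed 2-fold signals, gave 0.96 against 0.91 (gap 0.05) and 0.97 against 0.89 (gap 0.08). The overstatement is roughly 0.05 to 0.13.

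**5. DMRs.** If DMRs are chosen by response, as in Section 13.5, no threshold stands between noise and the model, and step 2 is the relevant guide. If they are chosen by treated against untreated samples, as in Appendix B, response labels are not used and that step leaks none.

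**The case against.** The strongest reply is that the plan does not say that selection is done once on all samples. It says that in each iteration "the remaining samples will be used to build a classifier", and building could include choosing features again. The risk-score algorithm is taken from a cited study whose steps the documents do not reproduce, and the synopsis also mentions supervised principal components. This stands: a reader might infer that leakage is a stated feature of the plan, but the text supports only that nesting is not required and that the written order points away from it.

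Second, near-perfect AUC on noise needs a top-k or nominal-p rule, which the plan does not contain. This also stands. A reader might infer that the plan would turn noise into an excellent signature; for RNA with a valid test, the usual result on noise would be no RNA feature to report. It does not remove the problem, because the filter does not cover DMRs and the bias persists once features pass.

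Third, "responders and non-responders after leflunomide treatment" may describe patients who did or did not respond, not specimens taken on drug. That is a fair reading, and the stated aim of baseline prediction supports it, so this part is a request for clarity.

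Fourth, the work is exploratory. No dose, stopping, eligibility or response-rate decision uses the classifier, and the documents do not say that it will select patients in later trials. That limits the weight of the point; it does not make an optimistic AUC correct.

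**Conclusion.** The point holds in limited form. Section 13.5 leaves open whether response-based selection is repeated in each fold, and an analyst who follows its order would report biased sensitivity, specificity and AUC. Under the RNA filter the likely size is an AUC overstated by roughly 0.05 to 0.13 when modest real signals exist, and a spurious RNA classifier in about 0 to 3% of pure-noise runs with an exact test, more with cruder tests and few responders. The 0.99 to 1.00 figure shows what an unfiltered screen can do; it is not a forecast for this plan. For DMRs the size cannot be given until the definition and threshold are fixed. These sizes depend on the assumed feature counts, independence, signal strength and model penalty. Correction is worthwhile because nesting is plainly the better method and costs almost nothing, but the primary response-rate conclusion does not depend on it.

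**What to change.** Amend Section 13.5 to state that:

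- every step that uses response status (the FDR and fold-change filter, any response-based DMR selection and any tuning) is repeated inside each LOOCV fold on the training samples only, with a rule for folds in which no feature passes;
- classifier features come only from baseline (pre-treatment) specimens, in line with the stated aim;
- one named DMR definition (Section 13.5 or Appendix B) feeds the model, with its threshold.

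Optional: report a permutation p-value from the same nested procedure, and delete the reference to random selection, since LOOCV leaves each patient out exactly once.

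The cost is a few sentences and a little computing time, with no change for patients. The reported AUC will probably be less favourable.
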